9.3. Phase I dose escalation phase

Cohorts of 3-6 patients each will be treated with escalating doses of copanlisib and ibrutinib (Table 9-2). If unforeseen toxicities are observed in 2 patients treated at dose level 1, the next cohort will be treated at dose level -1.

Table 9-2. Dose Escalation Levels			
No of pts	Cohort Level	Copanlisib (mg/dose)	Ibrutinib (mg/day)
3-6	-1	45	420
3-6	1	45	560
3-6	2	60	560

- At least 2 patients will be treated at each dose level. All patients treated at the preceding dose level will be observed at minimum of 28 days (1 cycle) before dose escalation occurs.
- Dose escalation will proceed as follows:
 - If none of the initial 3 patients in a cohort experiences dose limiting toxicity (DLT), then a new cohort of 3 patients will be treated at the next higher dose level.
 - If one of 3 patients in a cohort experiences DLT, then up to an additional 3 patients will be treated at the same dose level. Escalation will continue if only one of the 6 patients experiences a DLT.
 - In the event that ≥ 2 of 3 patients, or ≥ 2 of 6 patients in the first cohort experiences a DLT related to study drugs, then the next cohort of patients will be treated at a lower dose level (dose level -1) and no further dose escalation will occur in this step. Three patients will be enrolled at this dose level, if 0 or 1 patients experiences a study drug related DLT, a further 3 patients will be enrolled at this dose level. If overall 0 or 1 patient experiences a DLT at this dose level, this dose will be established as copanlisib/ ibrutinib maximum tolerated dose (MTD).
 - If ≥ 2 or more patients in the cohort experience DLT, then the maximum tolerated dose (MTD) will have been exceeded, and no further copanlisib and ibrutinib dose escalation will occur. The previous dose will be considered as the MTD.
 - If only 3 patients were treated at the dose level under consideration as the MTD, then up to an additional 3 patients will be accrued. If no more than 1 of 6 patients at that copanlisib and ibrutinib dose level experiences DLT, than that dose level will be confirmed as the MTD. If ≥ 2 or more patients in that cohort experience DLT, than the previous dose level will be studied in the same fashion.

The maximum tolerated dose (MTD) is the highest combination drug dosage not causing medically unacceptable DLT in $\geq 33\%$ (i.e. 2/6 patients) in the first cycle of treatment. The recommended phase II dose (RP2D) is the dose balancing clinical efficacy and toxicity.

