14.0 BIOSTATISTICS

14.1. Phase I

In the Phase I part the standard 3+3 dose escalation scheme will be used. If none of the initial cohort of 3 has a DLT (defined in Section 9.2) the dose level will be escalated. If one has a DLT that dose level will be expanded with 3 more patients. Dose escalation will stop if 2 or more DLTs are seen at a dose level within the treatment and observation periods as described in Section 9.2. The MTD is defined as the highest dose level at which at most 1 of the 6 patients treated at that level has a DLT. Two dose levels plus a "-1" dose level are planned for this study. The maximum sample size is 18 patients. Toxicity seen after 4 weeks that are likely or definitely related to treatment with study drugs will be collected and evaluated by the investigators.

All patients that stop protocol therapy or have dose reductions due to a DLT will be included in the DLT analysis. If a patient stopped therapy for other reasons and has taken $\leq 75\%$ of planned doses (2 of 3 copanlisib doses and 21 of 28 doses of ibrutinib) in the first cycle then they will be excluded from DLT analysis. In the event that a patient withdraws from the trial due to a reason unrelated to a DLT before completing cycle one, they will be replaced. We expect that less than 10% of patients will be replaced due to insufficient time of treatment. The probability of dose escalation based on various underlying DLT rates (Table 2).

Table 14-1. DLT probability table								
True DLT rate	5%	10%	15%	20%	25%	30%	40%	50%
Probability of escalation	0.97	0.91	0.81	0.71	0.60	0.49	0.31	0.17

It is expected that 2-3 patients will be enrolled per month and so the phase I portion of the trial will be completed in approximately 6 months.

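### One Section 9.3 bullet steps down to, and expands, dose level -1 on drug-related DLTs only, while Sections 9.2 and 14.1 count any DLT; the rules can give opposite instructions for the same data.

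*Combined protocol and SAP*

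**What the plan says.** **Section 9.2** lists the adverse events that count as DLTs in the first 28 days. It sets no condition on cause, and it bases the MTD on the incidence of DLT.

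**Section 14.1** refers back to that definition. On expansion: "If one has a DLT that dose level will be expanded with 3 more patients". The MTD is the highest level at which "at most 1 of the 6 patients treated at that level has a DLT".

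**Section 9.3, the step-down bullet**, has three linked rules:
- It opens level -1 when at least 2 patients "in the first cohort experiences a DLT related to study drugs".
- After 3 patients at level -1, "if 0 or 1 patients experiences a study drug related DLT, a further 3 patients will be enrolled at this dose level".
- The MTD sentence follows, with no qualifier: "If overall 0 or 1 patient experiences a DLT at this dose level", that dose becomes the MTD.

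**The other DLT-count bullets in Section 9.3** use the plain term. The next one says that with 2 or more DLTs in the cohort, "then the maximum tolerated dose (MTD) will have been exceeded". Two further sentences can also lead to level -1: the opening paragraph ("If unforeseen toxicities are observed in 2 patients treated at dose level 1") and the last bullet ("than the previous dose level will be studied in the same fashion").

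**Section 11.1.1** has relatedness recorded for each adverse event, so the qualifier can be applied in practice.

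**The concern.** Two counts are in use for one decision. They differ whenever a patient has a listed cycle 1 event that the investigator judges unrelated. The Section 9.2 list covers any grade 3 or higher non-hematologic event apart from stated exceptions, and any event causing a dose delay of more than 7 days. In relapsed mantle cell lymphoma some of these could plausibly be attributed to the disease or to another illness.

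At stake is whether 3 more patients are treated at level -1 after 2 or 3 of the first 3 have already had a DLT and, on one reading, whether that level can be accepted as the MTD when Sections 9.2 and 14.1 would reject it.

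**Working it through.** **1. Which count the plan's own figures use.** With true DLT rate q and no attribution filter, P(escalate) = (1−q)³ + 3q(1−q)² × (1−q)³.

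| q | 5% | 10% | 15% | 20% | 25% | 30% | 40% | 50% |
|---|---|---|---|---|---|---|---|---|
| Table 14-1 | 0.97 | 0.91 | 0.81 | 0.71 | 0.60 | 0.49 | 0.31 | 0.17 |
| Recomputed | 0.973 | 0.906 | 0.814 | 0.709 | 0.600 | 0.494 | 0.309 | 0.172 |

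All eight entries agree. The table corresponds to one DLT count applied without a filter, which under Section 9.2 as written is any DLT.

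**2. The conflict by counting.** Suppose 2 of the first 3 patients at level -1 have a DLT and one of the two is judged unrelated.
- Section 9.3 bullet: the related count is 1, so enrol 3 more.
- Section 14.1: the count is 2; expansion follows only one DLT, so do not expand.
- MTD sentence, read as any DLT: 2 of 6 is already certain, so at most 1 of 6 cannot be met. The 3 added patients cannot change the decision.
- MTD sentence, read as related DLTs only: the count is 1, and level -1 becomes the MTD if none of the next 3 has a related DLT. Sections 9.2 and 14.1 would reject it.

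This step needs no assumed rates, only that at least one DLT is judged unrelated.

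**3. How often the bullet expands after 2 or more DLTs.** Assumptions, not in the documents: q = 0.20 or 0.30 at every level; a share f = 0.1, 0.2 or 0.3 of DLT patients judged unrelated, independently.

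E = P(2 or 3 of the first 3 have a DLT, at most one related) = 3q²(1−q) × [1−(1−f)²] + q³ × [f³ + 3f²(1−f)].
- q = 0.20, f = 0.1: 0.096 × 0.19 + 0.008 × 0.028 = 0.0185
- q = 0.30, f = 0.3: 0.189 × 0.51 + 0.027 × 0.216 = 0.1022

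| | f = 0.1 | f = 0.2 | f = 0.3 |
|---|---|---|---|
| E, q = 0.20 | 0.018 | 0.035 | 0.051 |
| E, q = 0.30 | 0.037 | 0.071 | 0.102 |

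**4. How often level -1 is opened.** By any of the Section 9.3 routes, counting any DLT:
- Level 1 fails at first pass: A = 1 − P(escalate) = 0.291 (q = 0.20) or 0.506 (q = 0.30).
- Level 1 has 0 of 3, level 2 fails, and level 1 then fails on its 3 further patients: (1−q)³ × A × P(at least 2 of 3). This is 0.512 × 0.291 × 0.104 = 0.016, or 0.343 × 0.506 × 0.216 = 0.037.
- Sum: 0.307 or 0.543.

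**5. Per trial** (step 4 × step 3):
- Lowest: 0.307 × 0.0185 = 0.0057
- Highest: 0.543 × 0.1022 = 0.0555, or 0.056
- With first-pass failure alone: 0.0054 to 0.052
- With f = 0: exactly 0

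If level -1 (ibrutinib 420 mg instead of 560 mg) has a DLT rate 10 points lower than level 1, the first-pass figure falls to 0.002 to 0.03.

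**6. If the MTD sentence means related DLTs only.** Once level -1 is open, P(at most 1 of 6) is 0.655 at q = 0.20 and 0.420 at q = 0.30 on any DLT. On related DLTs (rate q(1−f)) it is 0.704 to 0.800 and 0.487 to 0.631 for f = 0.1 to 0.3. These are conditional on opening level -1, not per-trial figures.

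**The case against.** **The MTD sentence may carry the qualifier over.** It follows two sentences that specify related DLTs and may simply be shorthand. Section 9.3's own MTD definition speaks of a dosage not causing unacceptable DLT, which leans the same way, and the Section 14.2 stopping rules count treatment-related events. This stands as a possible reading. It makes the bullet consistent within itself but moves the conflict to Sections 9.2 and 14.1, which have no such condition. The documents do not settle which was meant.

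**Other text would stop the team.** Section 14.1 and the bullet that says the MTD has been exceeded both point away from expansion. That lowers the risk, but the latter expressly bars only further escalation, not more patients at level -1.

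**The patients may not be at real excess risk.** In this scenario at most one of the first 3 has a DLT judged drug-related, so it would be too strong to say that the combination has been shown to be toxic. That is fair. The defect is that the stated rules disagree.

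**Stronger readings that the documents do not support:**
- *An untested level -1 could become the MTD.* One might infer this where level 1 has 2 or more DLTs but fewer than 2 related, so that this bullet's step-down does not fire. The opening paragraph and the last bullet can still open level -1. Section 9.2 also limits the MTD to doses studied, and Section 14.1 to patients treated at the level.
- *Escalation to level 2 or Table 14-1 is distorted.* The escalation bullets count plain DLTs, and the table reproduces on that count.
- *A wrong phase II dose follows.* If the MTD sentence means any DLT, level -1 is still rejected. Only the related-only reading lets it through.

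**Conclusion.** The inconsistency is real and lies in current text. For identical data at level -1, the Section 9.3 bullet adds 3 patients and Section 14.1 does not. Depending on how the MTD sentence is read, the result is either 3 patients treated with no possible effect on the MTD decision, or a level accepted that Sections 9.2 and 14.1 reject.

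The expansion is rare: about 0.006 to 0.056 per trial over all routes to level -1, resting on the assumed DLT rates (20% to 30% at every level) and unrelated shares (10% to 30%), and 0 if every DLT is judged related. At most 3 extra patients are involved and the phase I maximum of 18 still holds. This is a minor correction to a safety rule.

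**What to change.** Use one DLT count throughout. In the step-down bullet of Section 9.3, delete the last four words of "in the first cohort experiences a DLT related to study drugs" and the three words that qualify DLT in the expansion sentence. That matches Sections 9.2 and 14.1.

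If attribution is intended, state it once in the Section 9.2 definition, so that Sections 9.3 and 14.1 both inherit it; Table 14-1 would then be read against the rate of related DLTs.

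The wording about unforeseen toxicities and medically unacceptable DLT elsewhere in Section 9.3 could be tidied at the same time, but this point does not need it.

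Cost: two short deletions in a protocol amendment. The sample size is unchanged, and under the plain count Table 14-1 stands as it is. Make the change before level -1 is opened.

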9.4. Phase II dose expansion

Patients will be enrolled at the MTD of copanlisib and ibrutinib combination. The safety events in the expansion cohorts will be reviewed on an ongoing basis by the primary investigator and several stopping rules are in place to protect patients from excessive toxicity (Section 14). Based on this review, we may adjust treating dose level to the RP2D.

Table 9-3. Phase II Simon two stage mini-max dose expansion cohorts

Disease	1 st stage	Response Needed	2 nd stage	Total Accrual
Mantle cell lymphoma	18 (include 6 patients from phase I study at MTD/RP2D)	If ≥ 5 patients with CR within 6 months, proceed to 2 nd stage	15	33 patients

9.5. Pharmacokinetics

Plasma concentrations of copanlisib, its metabolite M-1, and other metabolites if needed, and of ibrutinib will be measured at the following time points for pharmacokinetic (PK) assessment of patients in the phase I dose level 1 and 2 cohorts (see Table 9-4).

Table 9-4. Pharmacokinetic assessments

Cycle	Day	Planned time (h) after start of administration	Acceptable time window	Ibrutinib PK sampling	Copanlisib PK sampling	Ibrutinib dosing	Copanlisib dosing
1	15	0 (pre-dose)	- 30 min	X	X	X	X
		1 (end of Infusion) ^a	+ 5 min	X	X		
		1.5	\pm 15 min	X	X		
		2.5	\pm 30 min	X	X		
		3.5	\pm 30 min	X	X		
		4.5	\pm 30 min	X	X		
		6	\pm 30 min	X	X		

C_{max} = Maximal plasma concentration; EoI = End of infusion; PK = Pharmacokinetic(s).

a: The end of infusion sample for copanlisib and M-1 metabolite should be collected within 5 min after the end of infusion (EoI) of copanlisib for adequate characterization of C_{max} .

Samples should be collected at the planned time points as per Table 9-4, ideally within the allotted time windows. If samples are drawn outside the time window, it will not be considered a protocol deviation but the actual time of the blood draw should be noted. If clinically indicated, PK samples may be skipped without being considered a protocol deviation. For all samples, it is of importance that the actual date and time of blood sampling are documented in the eCRF because PK calculations will be based on the actual sampling times relative to dosing times.

Details about the collection, processing, storage and shipment of samples are provided separately in the Laboratory Manual.

9.6. Concomitant Medications

9.6.1 Permitted Concomitant Therapy

- Standard therapies for concurrent medical conditions
- Treatment with non-conventional therapies (for example herbs or acupuncture), and vitamin/mineral supplements is acceptable provided that they do not interfere with the study endpoints, in the opinion of the Investigator. St John's Wort is not permitted.
- Bisphosphonates
- Close monitoring is recommended according to standard of care. If either of these values is above the therapeutic range, the doses should be modified and the assessments should be repeated weekly until it is stable.
- Antiemetics: Prophylactic anti-emetics may be administered according to standard practice. The routine use of standard antiemetics, including steroids, 5-HT3 blockers, such as granisetron, ondansetron, or an equivalent agent, is allowed as needed.
- Palliative and supportive care for the other disease-related symptoms and for toxicity associated with treatment will be offered to all patients in this trial.
- Patients may receive palliative and supportive care for any underlying disease
- Palliative irradiation shall be permitted provided that:
 - In the opinion of the investigator, the patient does not have progression of disease.
 - The radiation field does not encompass a target lesion
 - The radiation field does not encompass a lung field (to reduce the risk for pneumonitis).
- Low-dose aspirin (maximum 100 mg/day) and low-dose heparin are permitted.
- Patients taking narrow therapeutic index medications should be monitored proactively, if these medications cannot be avoided. These medications may include quinidine, cyclosporine, and digoxin
- Short term systemic corticosteroids will be allowed for the management of acute conditions
- Use of neutrophil growth factors (filgrastim and pegfilgrastim) is not permitted in the dose escalation phase during cycle 1 unless a DLT has already been determined. Neutrophil growth factor support is allowed in the dose expansion portion of the study to treat neutropenia but not prophylactically.

9.6.2 Prohibited Concomitant Therapy

The following medications are prohibited during study treatment in the study (see Table 9-5 below):

This list is not comprehensive and is only meant to be used as a guide:

- Strong inhibitors or inducers of CYP3A4/5
- Other investigational and antineoplastic therapies
- Anti-arrhythmic therapy other than beta blockers or digoxin
- Ongoing immunosuppressive therapy
- Concomitant radiotherapy (it is assumed that radiation would be indicated only in case of progression, when the patient would come off study medication anyway)

- Herbal medications include, but not limited to: St. John's wort, Kava, ephedra (ma huang), gingko biloba, dehydroepiandrosterone (DHEA), yohimbe, saw palmetto, black cohosh and ginseng. Patients should stop using all herbal medications at least 7 days prior to first dose of study treatment.

Table 9-5: List of prohibited medications during the study

Category	Drug name
Strong CYP3A Inhibitors	Voriconazole, Boceprevir, clarithromycin, cobicistat, conivaptan, danoprevir/ritonavir, eltegravir/ritonavir, grapefruit juice, indinavir/ritonavir, itraconazole, ketoconazole, lopinavir/ritonavir, mibefradil, nefazodone, neflifavir, posaconazole, ritonavir, saquinavir, saquinavir/ritonavir, telaprevir, telithromycin, tipranavir/ritonavir, troleandomycin,
Moderate CYP3A Inhibitors	Grapefruit, grapefruit hybrids, pummelos, star-fruit, and Seville oranges (citrus paradisi fruit juice)
Strong CYP3A Inducers	Avasimibe, carbamazepine, mitotane, phenobarbital, phenytoin, rifabutin, rifampin (rifampicin), St. John's wort (hypericum perforatum)
Other Investigational and Antineoplastic Therapies	Other investigational therapies must not be used while the patient is on the study. Anticancer therapy (chemotherapy, biologic or radiation therapy, and surgery) other than the study treatments must not be given to patients while the patient is on the study medication. If such agents are required for a patient then the patient must be discontinued from the study.
Herbal Preparations/ Medications	Herbal preparations/medications should be reviewed for appropriateness and interactions throughout the study. These herbal medications include, but are not limited to: St. John's wort, Kava, ephedra (ma huang), gingko biloba, dehydroepiandrosterone (DHEA), yohimbe, saw palmetto, and ginseng. Patients should stop using these herbal medications 7 days prior to first dose of study drug
Palliative Radiotherapy	No dose modification of study treatment is needed during radiotherapy.

9.6.3 Drug-drug Interactions

Guideline for Use of CYP Inhibiting/Inducing Drugs

Both ibrutinib and copanlisib are metabolized primarily by CYP3A4. Plasma concentrations of ibrutinib and copanlisib may be increased from concomitant use of strong or moderate CYP3A4 inhibitors. Consequently, strong or moderate CYP3A4 inhibitor and inducers should be avoided. Ibrutinib and its major metabolite (dihydrodiol) have been shown, in vitro, to be weak inhibitors and inducers of CYP450 isoenzymes. Note that with the data available, it is not possible to confirm whether such interactions will occur in patients. Therefore, investigators, at their discretion, may administer concomitant medications known to be metabolized by

CYP3A4/5, CYP2C8, CYP2C9 and CYP2C19. The use of moderate and strong CYP3A inducers and inhibitors is strictly prohibited during the DLT evaluation period.

During phase II, strong inhibitors of CYP3A such as ketoconazole, indinavir, nelfinavir, ritonavir, saquinavir, clarithromycin, telithromycin, itraconazole, and nefazodone, etc should be avoided. If strong CYP3A inhibitors cannot be avoided, consider holding ibrutinib and copanlisib while on CYP3A inhibitor if it will be used short-term. Re-initiate ibrutinib and copanlisib after 5 to 6 half-life washout period of the CYP3A inhibitor. If concurrent therapy with strong inhibitors cannot be avoided, reduce the copanlisib dose to 45 mg. If antifungal therapy is required, strong inhibitors of CYP3A4, including ketoconazole, itraconazole, posaconazole, and voriconazole should be avoided. Moderate inhibitors of CYP3A4, such as isavuconazonium sulfate, may be used. If used with a moderate CYP3A4 inhibitor, ibrutinib dosing should be reduced to 140 mg daily. No dose adjustment to copanlisib is needed. Avoid grapefruit and Seville oranges during ibrutinib treatment, as these contain moderate inhibitors of CYP3A (see Appendix 1).

During phase II, strong inducers of CYP3A such as enzyme-inducing anti-epileptics (carbamazepine, phenytoin, etc), rifampin, and St. John's Wort etc, should be avoided. Co-administration of ibrutinib with strong CYP3A inducers, rifampin, in healthy subjects decrease ibrutinib plasma concentrations by approximately 10-fold. Consider alternative agents with less CYP3A induction. If strong CYP3A inducers cannot be avoided, consider holding ibrutinib and copanlisib while on CYP3A inducer if it will be used short-term. Re-initiate ibrutinib and copanlisib after 5 to 6 half-life washout period of the CYP3A inducer. Additionally, corticosteroid doses more than 4mg oral daily of dexamethasone-equivalent (>26mg prednisone) may induce CYP3A enzyme, so need to be discussed with investigators.

A list of common, moderate to strong, CYP3A inhibitors or inducers is provided in the appendices; a comprehensive list of inhibitors, inducers, and substrates may be found at <http://medicine.iupui.edu/clinpharm/ddis/main-table/>. This website is continually revised and should be checked frequently for updates (Appendix 1).

Sensitive substrates of CYP3A should be used with caution. A comprehensive list of sensitive substrates of CYP3A could be found on FDA website: <https://www.fda.gov/drugs/developmentapprovalprocess/developmentresources/druginteractionslabeling/ucm093664.htm#table3-1>.

Concomitant Use of Antiplatelet Agents and Anticoagulants

Ibrutinib may increase the risk of hemorrhage in patients receiving antiplatelet or anticoagulant therapies. The mechanism for this bleeding is not well understood.

Warfarin or vitamin K antagonists should not be administered concomitantly with ibrutinib or copanlisib. Supplements such as fish oil and vitamin E preparations should be avoided. Use ibrutinib with caution in subjects requiring other anticoagulants or medications that inhibit platelet function.

Subjects receiving antiplatelet agents in conjunction with ibrutinib should be observed closely for any signs of bleeding or bruising and ibrutinib should be withheld in the event of any bleeding events.

Subjects requiring the initiation of anticoagulation therapy (other than warfarin or a vitamin K antagonist, which should be avoided) during the course of the study should have treatment with ibrutinib held, the PI should be contacted, and ibrutinib should not be restarted until the subject is clinically stable. Subjects should be observed closely for signs and symptoms of bleeding.

Subjects were excluded from participation in ibrutinib Phase 2 and 3 studies if they required warfarin or other vitamin K antagonists. Therefore, ibrutinib should not be administered concomitantly with warfarin or other vitamin K antagonists. Ibrutinib should be used with caution in patients requiring other anticoagulants or medications that inhibit platelet function. Patients receiving antiplatelet agents in conjunction with ibrutinib should be observed closely for any signs of bleeding or bruising and ibrutinib should be withheld in the event of any bleeding events. Supplements such as fish oil and vitamin E preparations should be avoided. Patients with congenital bleeding diathesis have not been studied.

